*The maximum duration of therapy is 24 months. If the patient achieves CR during this period, further pembrolizumab cycles will be discontinued and the patient will proceed to survival followup.

**Non-responders include patients with progressive, nodal, visceral, or blood disease as assessed by repeat staging after Cycle 4 and at the end of treatment visit.

Generic name: pembrolizumab, MK-3475
Brand name(s): Keytruda™
Mayo Abbreviation: MK3475
Availability: Mayo Clinic Pharmacy

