11.2 Evaluation of Measurable Disease

11.21 Evaluation of primary cutaneous lesion

mSWAT is calculated using body surface area (BSA) of each MF lesion (palm plus fingers of the patient $\approx 1\%$ BSA) in each of 12 areas of the body, multiplying the sum of the BSA of each lesion type by a weighting factor (patch=1, plaque=2, and tumor =4) and generating a sum of the subtotals of each lesion subtype.

11.211 Measurement of effect

- Overall cutaneous response rate (ORR) = proportion of patients with a 50% or greater reduction of baseline mSWAT score
- Complete cutaneous response rate (CR) = proportion of patients with a 100% reduction of baseline mSWAT score
- Cutaneous 90 response rate (CR90) = proportion of patients with a 90% or greater reduction of baseline mSWAT score without the development of new tumors
- Cutaneous partial response rate (PR) = proportion of patients with a 50-90% baseline reduction of mSWAT score without the development of new tumors
- Progressive cutaneous disease (PD) = greater than 25% increase in baseline mSWAT or the development of new tumors. However, if in the judgement of the investigator, the increase in mSWAT is the result of inflammation due to treatment and/or the unmasking of subclinical skin involvement, this increase in mSWAT shall not be considered evidence of progressive cutaneous disease and the patient shall otherwise be classified as stable cutaneous disease (SD).
- Stable cutaneous disease (SD) = <25% increase to <50% reduction in baseline mSWAT without the development of new tumors ; or patients with a greater than 25% increase baseline mSWAT due to

the result of inflammation due to treatment and/or the unmasking of subclinical skin involvement.

- Relapsed cutaneous disease = Any disease recurrence in those with complete response

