13.1 Continuation of treatment

Patients who are CR90, PR, or SD will continue treatment per protocol up to a maximum duration of 24 months..

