13.2 Progressive disease (PD)

Patients who develop PD (non-responders) during cycle 1 will exit the study (no follow-up). Patients who develop PD subsequent while receiving therapy will complete the End of Treatment visit at the time of PD and repeat staging per protocol, then proceed to survival follow-up (Section 4.2).

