16.0 Statistical Considerations and Methodology

16.1 Overview

This is a phase II study designed to assess the overall cutaneous response rate at cycle 9 in MF patients treated with pembrolizumab. It is a single one-stage design with an interim analysis based on the Simon optimal design with 85% power and 10% Type I error.

NOTE: As per Amendment 4, accrual will cease after the enrollment of 10 patients due to sponsor decision on funding. Thus, the study power and type I error will not be appropriate for the analysis, as the study will not be able to go to full accrual. The study will be analyzed at the pre-defined interim step.

16.11 Endpoint:

The primary endpoint is overall cutaneous response (cutaneous complete response (CR), cutaneous 90 response (CR90) or cutaneous partial response (PR)) as defined using the mSWAT score as stated in section 11.0. Throughout Section 16.0, CR, CR90 or PR will be considered synonymous with “success”, unless specified otherwise. All patients meeting the eligibility criteria who have signed a consent form and have begun treatment will be evaluable for response.

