16.2 Statistical Design

- 16.21 Design: The largest success proportion where the proposed treatment regimen would be considered ineffective in this population is 15%, and the smallest success proportion that would warrant subsequent studies with the proposed regimen in this patient population is 35%. This design uses 28 evaluable patients to test the null hypothesis that the true complete response rate is at most 15%.
- 16.22 Interim Analysis: Enter 10 evaluable patients to the study. If there are less than 2 successes in the first 10 evaluable patients, we will consider this regimen ineffective in this patient population and terminate this study. Otherwise, if the number of successes is at least 2, we will continue accrual.
- 16.23 **N/A as per Amendment 4:** Final Decision rule: If 6 or fewer successes are observed in the first 28 evaluable patients, we will consider this regimen ineffective in this patient population. Otherwise, if the number of successes is at least 7, this will be considered evidence of promising activity and the treatment may be recommended for further testing in subsequent studies.
- 16.24 **N/A as per Amendment 4:** NOTE: We will not suspend accrual at the interim analysis to allow the first 10 patients to become evaluable, unless undue toxicity is observed. Given the limited overall sample size and the inclusion of an adverse events stopping rule, we feel it is ethical to not halt accrual for the interim analysis. However, if accrual is extremely rapid, we may temporarily suspend accrual in order to obtain safety data on these patients before re-opening accrual to further patients.

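### A patient taken off treatment for nodal, visceral or blood progression at about week 13 can still be scored a cycle 9 success, because 16.41 does not clearly stop an earlier mSWAT response being carried forward

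*Combined protocol and SAP*

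**What the plan says.** The combined protocol and SAP uses two vocabularies for response.

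- **Disposition.** The schema footnote reads "Non-responders include patients with progressive, nodal, visceral, or blood disease as assessed by repeat staging after Cycle 4" and goes on to include staging at the end of treatment. Section 13.2 puts the same label on progressive disease and says: "Patients who develop PD subsequent while receiving therapy will complete the End of Treatment visit at the time of PD". Survival follow-up comes next. Section 11.0 counts nodes, viscera and blood towards progression, and Section 7.1 ends treatment at progression. Section 13.1 says "Patients who are CR90, PR, or SD will continue treatment per protocol up to a maximum duration of 24 months", without saying whether that status is cutaneous or overall.
- **Primary endpoint.** Section 16.11 defines it as "overall cutaneous response (cutaneous complete response (CR), cutaneous 90 response (CR90) or cutaneous partial response (PR)) as defined using the mSWAT score". It adds that "CR, CR90 or PR will be considered synonymous with" success throughout Section 16. The overall cutaneous response rate in Section 11.211 is the "proportion of patients with a 50% or greater reduction of baseline mSWAT score". Neither section excludes a patient with extracutaneous progression, and every eligible, consented, treated patient is evaluable.
- **Early exits.** Section 16.41 compares mSWAT at baseline and cycle 9. It carries the last observation forward for participants who withdraw, are lost, or leave the study as the protocol provides.
- **Systemic response.** Section 11.5 requires the same mSWAT fall with no progressive nodal, visceral or blood involvement. Section 16.42 reports it as a secondary proportion.
- **Decision rule.** Under Section 16.22, "If there are less than 2 successes in the first 10 evaluable patients", the regimen is judged ineffective. Under Amendment 4 accrual stops at 10, the final 28-patient rule no longer applies, and the study is analysed at this step.

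**The concern.** A patient can leave treatment because the lymphoma has progressed, carry the label non-responder in the schema and in 13.2, and still enter the primary analysis as a cycle 9 success on a skin score taken before or at the time of stopping. The primary goal (Section 2.1) is antitumor activity, and 2 of 10 is the only efficacy criterion still in force. With so small a threshold, each such patient is half of what is needed. The error can run only one way: carrying the score forward can add successes but cannot remove any. The case is foreseeable, because Section 3.12 admits stage IV disease and Sézary syndrome, although 3.39a excludes Sézary patients whose blood burden needs immediate cytoreduction.

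**Working it through.** **Timing.** A cycle is 21 days (Section 4.1).

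- End of cycle 4: 4 × 3 = week 12. Restaging is one week later, at week 13.
- End of cycle 9: 9 × 3 = week 27, which matches the week 27 endpoint in Section 1.23.
- This is the only restaging scheduled before cycle 9 for a patient still on treatment.

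**One patient followed through the text.** Take a 55% fall in mSWAT and blood progression (Section 11.31) at week 13.

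1. Schema footnote and 13.2: non-responder.
2. Sections 7.1 and 13.2: treatment ends, an End of Treatment visit with mSWAT takes place, then survival follow-up.
3. The 30- and 90-day clinical follow-up visits are described in 13.4 and 13.6 for patients who completed 24 months, so no cycle 9 mSWAT is scheduled for this patient.
4. Section 16.11: the patient is evaluable and stays in the denominator.
5. Section 16.41: if the carry-forward applies, the 55% fall becomes the cycle 9 value and the patient is a success.

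Step 5 is not fully explicit. Sections 13.2 and 13.3 speak of exiting the study for progression in cycle 1 and for alternative therapy, whereas later progression leads to survival follow-up. The natural reading of 16.41 still carries the score forward. On the other reading, the plan gives an evaluable patient no scoring rule.

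**The plan's own figure.** With n = 10 and true success rate p, the chance of passing is

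P(X ≥ 2) = 1 − (1 − p)^10 − 10p(1 − p)^9.

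At p = 0.15: 1 − 0.1969 − 0.3474 = 0.456. The formula also gives 0.624, 0.756, 0.851 and 0.914 at p = 0.20, 0.25, 0.30 and 0.35. All five agree with the table in Section 16.33.

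**Effect of the scoring choice.** Let f be the share of skin responders (carry-forward included) who stopped for extracutaneous progression before cycle 9. Excluding them changes p to p(1 − f). The documents do not give f; 10% to 30% is assumed.

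| Skin rate p | f | p(1 − f) | P(≥2 of 10), counted | P(≥2 of 10), excluded | Difference |
|---|---|---|---|---|---|
| 0.15 | 10% | 0.135 | 0.456 | 0.399 | 0.056 |
| 0.15 | 20% | 0.120 | 0.456 | 0.342 | 0.114 |
| 0.15 | 30% | 0.105 | 0.456 | 0.283 | 0.172 |
| 0.35 | 10% | 0.315 | 0.914 | 0.873 | 0.041 |
| 0.35 | 20% | 0.280 | 0.914 | 0.817 | 0.097 |
| 0.35 | 30% | 0.245 | 0.914 | 0.745 | 0.170 |

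Differences are taken before rounding. Successes under the stricter scoring are a subset of the others, so the last column is also the probability that the two scorings give opposite answers to the 2-of-10 rule.

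**The case against.** The strongest reply is that the primary endpoint is not in conflict with itself. Sections 1.23, 11.0, 11.211 and 16.11 all make it cutaneous, and 11.5 with 16.42 gives the extracutaneous question its own secondary endpoint. The footnote belongs to a treatment schema, its companion footnote concerns disposition, and nothing in Section 16 tells an analyst to use it. All of that stands, and it limits what may be concluded. Several stronger readings are tempting, but the documents do not support them:

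- *The primary endpoint should become a composite for everyone.* The skin-only choice is deliberate, and replacing it is a design trade-off.
- *The conflict has nothing to do with missing scores.* The two labels do differ whatever data are in hand, but the practical case does turn on missing data. The week 13 patient has no scheduled cycle 9 mSWAT and becomes a success only through carry-forward.
- *One such patient passes the rule.* That patient supplies one of two successes.
- *The chance of exactly two successes (0.276 at 15%, 0.302 at 20%) is the chance that such a patient decides the result.* Those figures count two successes of any kind.
- *Stable nodal, visceral or blood disease is a non-response, or month 24 staging can overturn a week 27 response.* The first rests on a stray comma, which 11.5 and 13.1 resolve. The second gives the footnote an analysis role it does not have.

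The stakes are also lower than under the full design. Accrual ends at 10 in any case, and Section 16.1 concedes that the stated power and type I error no longer apply. The rule now governs interpretation only.

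The reply leaves one gap unanswered: a cutaneous endpoint at cycle 9 does not by itself justify giving a cycle 9 response to someone who stopped for progression 14 weeks earlier (27 − 13).

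**Conclusion.** The concern holds as a gap in the scoring of early progression. The plan does not clearly say how to score a skin responder who stops for extracutaneous progression before cycle 9, and its natural reading counts that patient as a success, against its own non-responder label. The bias is upward and bears on the one efficacy criterion left. Its size depends on a share the documents do not give. At an assumed 10% to 30% of skin responders, the chance of passing at a 15% skin rate is 0.399 to 0.283 with these patients excluded, against 0.456 with them counted. If no such patient occurs, nothing changes. The calculation treats patients as independent with a common response rate. The point should be settled before the analysis; it does not undermine the choice of a cutaneous endpoint.

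**What to change.** 1. In Section 16.41, state that a patient who stops treatment for documented progression in skin, nodes, viscera or blood before the cycle 9 assessment is counted as not a success, stays in the denominator, and has no earlier mSWAT response carried forward.
2. Keep the cutaneous endpoint otherwise. Beside the primary 2-of-10 count, show the count under the Section 11.5 systemic definition.
3. In the schema footnote, remove the comma after the word progressive, so that it qualifies nodal, visceral and blood disease in line with 11.5 and 13.1. Mark non-responder there as a disposition term that does not reclassify cycle 9 response.
4. Reconcile 13.1 with 13.2 by saying whether the status named in 13.1 is cutaneous or overall. Which disposition is intended is for the clinical team.

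The cost is protocol and SAP wording, using staging and mSWAT already collected. The reported primary rate may be slightly lower, and so may the chance of passing when the drug works: at a 35% skin rate, 0.873 to 0.745 instead of 0.914 under the same assumed shares. Because Section 16.61 has the statistician reviewing endpoints weekly, date the change and report how many patients it affects.

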1.0 Background

Mycosis fungoides (MF) is an incurable extranodal, T-cell non-Hodgkin lymphoma that accounts for 80% of all primary cutaneous lymphomas. Affected individuals initially develop pruritic patches initially in sun protected anatomic sites. Most presentations are indolent but 20% progress in a stepwise fashion from patch disease to raised plaque and nodular skin lesions with variable degrees of lymph node, blood, and visceral organ involvement (Wilcox, 2017).

Patients who fail skin directed therapies receive systemic therapy with bexarotene, interferon, extracorporeal photopheresis, deacetylase inhibitors, methotrexate, pralatrexate, gemcitabine, pegylated liposomal doxorubicin, bortezomib, and denileukin dititox (Devata et al., 2016; Trautinger, 2017). These agents may be combined after the failure of monotherapy or rotated therapeutically if toxicity or efficacy limits use.

Patients with advanced stage disease have a 5-year survival of 17-40%, and ultimately die of lymphoma and infectious complications associated with disease progression after 2-3 lines of systemic therapy.

Pembrolizumab, an immune checkpoint inhibitor of PD-1, has been recently reported to have clinical activity in MF previously treated with one systemic agent and also in patients with Sézary syndrome (SS) (Khodadoust et al., 2016).

Pembrolizumab is presently FDA approved for the treatment of unresectable or metastatic melanoma, as first-line treatment of patients with metastatic non-small cell lung cancer (NSCLC) with high PD-L1 expression, recurrent or metastatic head and neck squamous cell carcinoma (HNSCC) with disease progression, and in refractory classical Hodgkin lymphoma (cHL) who have relapsed after three or more prior lines of therapy.

1.1 Pharmaceutical and Therapeutic Background

The importance of intact immune surveillance in controlling outgrowth of neoplastic transformation has been known for decades. Accumulating evidence shows a correlation between tumor-infiltrating lymphocytes (TILs) in cancer tissue and favorable prognosis in various malignancies. In particular, the presence of CD8+ T-cells and the ratio of CD8+ effector T-cells / FoxP3+ regulatory T-cells seems to correlate with improved prognosis and long-term survival in many solid tumors.

The PD-1 receptor-ligand interaction is a major pathway hijacked by tumors to suppress immune control. The normal function of PD-1, expressed on the cell surface of activated T-cells under healthy conditions, is to down-modulate unwanted or excessive immune responses, including autoimmune reactions. PD-1 (encoded by the gene Pdcd1) is an Ig superfamily member related to CD28 and CTLA-4 which has been shown to negatively regulate antigen receptor signaling upon engagement of its ligands (PD-L1 and/or PD-L2).

The structure of murine PD-1 has been resolved. PD-1 and family members are type I transmembrane glycoproteins containing an Ig Variable-type (V-type) domain responsible for ligand binding and a cytoplasmic tail which is responsible for the binding of signaling molecules. The cytoplasmic tail of PD-1 contains 2 tyrosine-based signaling motifs, an immunoreceptor tyrosine-based inhibition motif (ITIM) and an immunoreceptor tyrosinebased switch motif (ITSM).

Following T-cell stimulation, PD-1 recruits the tyrosine phosphatases SHP-1 and SHP-2 to the ITSM motif within its cytoplasmic tail, leading to the dephosphorylation of effector molecules such as CD3 ζ , PKC θ and ZAP70 which are involved in the CD3 T-cell signaling cascade. The mechanism by which PD-1 down modulates T-cell responses is similar to, but distinct from that of CTLA-4 as both molecules regulate an overlapping set of signaling proteins. PD-1 was shown to be expressed on activated lymphocytes including peripheral CD4+ and CD8+ T-cells, B-cells, Tregs and Natural Killer cells. Expression has also been shown during thymic development on CD4-CD8- (double negative) T-cells as well as subsets of macrophages and dendritic cells. The ligands for PD-1 (PD-L1 and PD-L2) are constitutively expressed or can be induced in a variety of cell types, including non-hematopoietic tissues as well as in various tumors. Both ligands are type I transmembrane receptors containing both IgV- and IgC-like domains in the extracellular region and contain short cytoplasmic regions with no known signaling motifs.

Binding of either PD-1 ligand to PD-1 inhibits T-cell activation triggered through the T-cell receptor. PD-L1 is expressed at low levels on various non-hematopoietic tissues, most notably on vascular endothelium, whereas PD-L2 protein is only detectably expressed on antigen-presenting cells found in lymphoid tissue or chronic inflammatory environments.

PD-L2 is thought to control immune T-cell activation in lymphoid organs, whereas PD-L1 serves to dampen unwarranted T-cell function in peripheral tissues. Although healthy organs express little (if any) PD-L1, a variety of cancers were demonstrated to express abundant levels of this T-cell inhibitor. PD-1 has been suggested to regulate tumor-specific T-cell expansion in subjects with melanoma (MEL). This suggests that the PD-1/PD-L1 pathway plays a critical role in tumor immune evasion and should be considered as an attractive target for therapeutic intervention.

Pembrolizumab is a potent and highly selective humanized monoclonal antibody (mAb) of the IgG4/kappa isotype designed to directly block the interaction between PD-1 and its ligands, PD-L1 and PD-L2. KeytrudaTM (pembrolizumab) has recently been approved in the United States for the treatment of patients with unresectable or metastatic melanoma and disease progression following ipilimumab and, if BRAF V600 mutation positive, a BRAF inhibitor.

1.2 Rationale

1.21 Rationale for the Trial and Selected Subject Population

There is no evidence-based algorithm for the treatment of MF, but therapies have been conventionally divided into skin-directed therapy and systemic therapy. Patients with early stage disease (patch/plaque disease without nodal or visceral involvement) are treated with topical corticosteroids, topical cytostatic agents, topical retinoids, superficial radiotherapy, and phototherapy. These modalities are rarely remittive but may temporarily clear involved skin and improve pruritus.

For progressive early stage MF, high risk early-stage MF (thick plaques or follicular involvement), advanced-stage MF (presence of tumors, nodal involvement, erythroderma, visceral involvement), or SS, systemic therapy is the standard of care. Biologic response modifying agents such as IFN-alpha, bexarotene, or HDAC inhibitors are considered first line, as systemic multi-agent chemotherapy provides no survival advantage.

However, the optimal treatment sequence is unknown and there is no clear evidence that sequential or step-wise combination systemic therapy is more efficacious or contributes to long-term survival or cure. Early/initial use of pembrolizumab in the treatment of advanced MF is postulated to have a unique therapeutic synergy, whereby the direct reduction of tumor burden by pembrolizumab further enhances the baseline endogenous host anti-tumor response that is subsequently amplified with additional scheduled treatments. This rationale supports the use of pembrolizumab as initial first line systemic therapy, as the endogenous anti-tumor host response is more robust earlier in the disease course and is thus more likely to produce clinical clearance of lesional skin.

1.22 Rationale for Dose Selection, Regimen, and Modification

Multiple prior studies have been conducted to evaluate the safety and clinical activity of single agent pembrolizumab. The dose escalation portion of this trial evaluated three dose levels, 1 mg/kg, 3 mg/kg, and 10 mg/kg, administered every 2 weeks (Q2W) in subjects with advanced solid tumors. All three dose levels were well tolerated and no dose limiting toxicities were observed. Recent data from other clinical studies within the pembrolizumab program has shown that a lower dose of pembrolizumab and a less frequent schedule may be sufficient for target engagement and clinical activity.

PK data analysis of pembrolizumab administered Q2W and Q3W showed slow systemic clearance, limited volume of distribution, and a long half-life (refer to IB). Pharmacodynamic data (IL-2 release assay) suggested that peripheral target engagement is durable (>21 days). This early PK and pharmacodynamics data provides scientific rationale for testing a Q2W and Q3W dosing schedule.

A population pharmacokinetic analysis has been performed using serum concentration time data from 476 patients. Within the resulting population PK model, clearance and volume parameters of pembrolizumab were found to be dependent on body weight. The relationship between clearance and body weight, with an allometric exponent of 0.59, is within the range observed for other antibodies and would support both body weight normalized dosing or a fixed dose across all body weights. pembrolizumab has been found to have a wide

therapeutic range based on the melanoma indication. The differences in exposure for a 200 mg fixed dose regimen relative to a 2 mg/kg Q3W body weight based regimen are anticipated to remain well within the established exposure margins of 0.5 – 5.0 for pembrolizumab in the melanoma indication. The exposure margins are based on the notion of similar efficacy and safety in melanoma at 10 mg/kg Q3W vs. the proposed dose regimen of 2 mg/kg Q3W (i.e. 5-fold higher dose and exposure). The population PK evaluation revealed that there was no significant impact of tumor burden on exposure. In addition, exposure was similar between the NSCLC and melanoma indications. Therefore, there are no anticipated changes in exposure between different indication settings.

The rationale for further exploration of 2 mg/kg and comparable doses of pembrolizumab in solid tumors is based on: 1) similar efficacy and safety of pembrolizumab when dosed at either 2 mg/kg or 10 mg/kg Q3W in melanoma patients, 2) the flat exposure-response relationships of pembrolizumab for both efficacy and safety in the dose ranges of 2 mg/kg Q3W to 10 mg/kg Q3W, 3) the lack of effect of tumor burden or indication on distribution behavior of pembrolizumab (as assessed by the population PK model) and 4) the assumption that the dynamics of pembrolizumab target engagement will not vary meaningfully with tumor type.

The choice of the 200 mg Q3W as an appropriate dose for the switch to fixed dosing is based on simulations performed using the population PK model of pembrolizumab showing that the fixed dose of 200 mg every 3 weeks will provide exposures that 1) are optimally consistent with those obtained with the 2 mg/kg dose every 3 weeks, 2) will maintain individual patient exposures in the exposure range established in melanoma as associated with maximal efficacy response and 3) will maintain individual patients exposure in the exposure range established in melanoma that are well tolerated and safe.

A fixed dose regimen will simplify the dosing regimen to be more convenient for physicians and to reduce potential for dosing errors. A fixed dosing scheme will also reduce complexity in the logistical chain at treatment facilities and reduce wastage.

